3.3 Study Duration, Enrollment and Number of Sites

3.3.1 Duration of Study Participation

The study duration per subject will be up to 90 days, with up to 1 day for screening, up to 2 days for Phase 1 (Intervention Phase), and up to 89 subsequent days (or until hospital discharge, whichever comes first) for follow-up.

3.3.2 Total Number of Study Sites/Total Number of Subjects Projected

The study will be conducted at one investigative site in the United States (the Children's Hospital of Philadelphia). The University of Utah will act as the Data Coordinating Center (DCC) for this study, but they will not be engaged in human subjects research. Their role is limited to the receipt of a limited dataset from the CHOP investigators.

Recruitment will stop when 70 subjects are enrolled and randomized. It is expected that approximately 80 eligible subjects will be enrolled to produce 70 evaluable subjects.

3.4 Study Population

Eligibility criteria are designed to enroll a broad, heterogeneous cohort of pediatric patients with suspected septic shock who are easily recognizable within routine clinical practice and

are representative of the broader population of pediatric patients treated for suspected septic shock.

3.4.1 Inclusion Criteria

- 1) Males or females age ≥ 6 months to <18 years
- 2) Clinician concern for septic shock, operationalized as:
 - a) a “positive” ED sepsis alert confirmed at the physician led “sepsis huddle” OR
 - b) a physician diagnosis of suspected septic shock requiring parenteral antibiotics and fluid resuscitation as per the ED sepsis management pathway

NOTE: Condition 2a above is met by:

- A. Tachycardia or hypotension for age *AND*
- B. Fever (home or ED >38 °F), hypothermia, or other signs/symptoms of infection *AND*

At least one of C, D, or E

- C. Flash (< 1 second) or delayed (>3 seconds) capillary refill
- D. Altered mental status
- E. Existing high-risk condition, including:
 - i. <56 days-old
 - ii. Asplenia
 - iii. Bone marrow or solid organ transplant
 - iv. Central venous catheter
 - v. Malignancy
 - vi. Significant neurological dysfunction or technological dependence at baseline
 - vii. Other immunodeficiency or immunocompromised

As per the existing CHOP ED Sepsis Alert, the presence of A *and* B *and* either C, D, or E will be determined by the triage nurse (and then continuously by the ED treating nurse if criteria are not initially met). If these criteria are met, then a “sepsis huddle” will be called with immediate physician bedside patient evaluation for possible septic shock. Patients who are considered to have suspected septic shock will be treated on the CHOP ED sepsis management protocol (Appendix 5) and will be considered for study eligibility

NOTE: Condition 2b above is met by any patient who does not meet criteria for a “sepsis huddle” but is diagnosed by the treating ED physician with suspected septic shock requiring parenteral antibiotics and fluid resuscitation.

Combining both the nurse-driven electronic sepsis alert with physician judgement to identify suspected septic shock in the CHOP emergency department, we have documented a 99.4% sensitivity and 99.1% specificity to identify patients who met international consensus criteria for severe sepsis/septic shock while only 5.5% of ED patients who developed severe

sepsis/septic within 24 hours of ED presentation were missed.⁴⁸ However, because the positive predictive value of this combined approach was 25.4%, we have required the additional inclusion criterion of administration of at least 20 mL/kg IV/IO fluid resuscitation with additional fluid deemed likely to be necessary to treat poor perfusion, defined as either hypotension or abnormal (either “flash” or >3 second) capillary refill (as determined by clinician’s judgment).

- 3) Administration of at least 20 mL/kg IV/IO fluid resuscitation
- 4) Receipt of ≤ 40 mL/kg IV/IO crystalloid fluid prior to randomization
- 5) Additional fluid deemed likely to be necessary to treat poor perfusion, defined as either hypotension or abnormal (either “flash” or >2 second) capillary refill (as determined by clinician’s judgment)¹⁰

NOTE: Due to the pragmatic nature of this study that is designed to reflect usual clinical practice, we will not define specific thresholds for either hypotension or abnormal capillary refill but rather defer to the treating clinician’s discretion to determine hypotension and abnormal capillary refill.

- 6) Parental/guardian permission (informed consent) if time permits; otherwise, EFIC criteria met

NOTE: For patients who may be transferred to the CHOP ED from an outside facility, many will have started fluid resuscitation prior to arrival in the CHOP ED. If volume of crystalloid fluid administration cannot be easily determined such that receipt of ≤ 40 mL/kg IV/IO crystalloid volume cannot be easily verified, these patients will be operationalized as not meeting the ≤ 40 mL/kg inclusion criterion.

NOTE: Patients who are randomized to a study arm at ≤ 40 mL/kg crystalloid fluid resuscitation *but for whom study fluid is not initiated until after >40 mL/kg* will still be included and should commence with administration of study fluid for the duration of the remaining intervention phase.

3.4.2 Exclusion Criteria

Reflecting the pragmatic design of the proposed study, exclusion criteria are purposely limited to ensure maximal external validity. FDA listed “contraindications” to LR are reflected as absolute exclusions (e.g., age < 6 months), while FDA listed “warnings” and “precautions” to LR administration are incorporated into the below listed exclusion criteria (see Table 2 in Section 1.4 for summary of FDA recommendations for use of LR in the pediatric and critically ill population). In addition, exclusion criteria are operationalized to reflect the common clinical practice (and guideline recommendations) to begin administration of either NS or LR to resuscitate septic shock without delays imposed by waiting for laboratory diagnostic tests.

- 1) Clinician judgement that patient's condition deems it unsafe to administer either NS or LR (since patients will be equally likely to receive NS or LR at time of study enrollment), including (but not limited to):
 - a) Clinical suspicion for impending brain herniation based on data available at or before patient meets criteria for study enrollment
 - b) Known hyperkalemia, defined as non-hemolyzed whole blood or plasma/serum potassium > 6 mEq/L, based on data available at or before patient meets criteria for study enrollment
 - c) Known hypercalcemia, defined as plasma/serum total calcium > 12 mg/dL or whole blood ionized calcium > 1.35 mmol/L, based on data available at or before patient meets criteria for study enrollment
 - d) Known acute fulminant hepatic failure, defined as plasma/serum ALT $> 10,000$ U/L or total bilirubin > 12.0 mg/dL, based on data available at or before patient meets criteria for study enrollment
 - e) Known history of severe hepatic impairment, defined as diagnosis of cirrhosis, "liver failure", or active listing for liver transplant
 - f) Known history of severe renal impairment, defined as current dependency on peritoneal dialysis or hemodialysis
 - g) Known metabolic disorder, inborn error of metabolism, or primary mineralcorticoid deficiency (e.g., mitochondrial disorder, urea cycle disorder, amino acidemia, fatty acid oxidation disorder, glycogen storage disorder, congenital adrenal hypoplasia, Addison's disease) as reported by subject, LAR or accompanying caregiver, or as listed in the medical record

NOTE: Due to the short therapeutic time window available for fluid resuscitation—and therefore study enrollment (see Section 3.1.1.)—in pediatric septic shock, it is not feasible to wait for diagnostic tests to identify medical conditions. Therefore, exclusion will be based on medical conditions that are known (or, in the case of impending brain herniation, suspected) at or before the time a patient otherwise meets criteria for study enrollment. If such data are not available and the treating clinician does not otherwise, in his/her best judgement, deem it unsafe to administer either NS or LR, then the patient will be eligible for study enrollment if they meet all other inclusion and exclusion criteria. Given the dynamic nature of sepsis, should an enrolled subject be noted to have a condition for which further administration of either NS or LR is deemed to be unsafe, the subject will be withdrawn from further study fluid administration. Because potassium, calcium, and liver function tests are already measured in all patients with suspected septic shock as part of routine care, there is no specific mandate to measure these values for the sole purposes of this study.

- 2) Known pregnancy determined by routine clinical history disclosed by patient and/or LAR (or other accompanying acquaintance)

NOTE: The exclusion of pregnant women is indicated under the provisions for "exception from informed consent" rather than a specific need to exclude pregnancy women from the interventions to be tested in this study. Given the absence of data or plausible adverse biological effect for either NS or LR in pregnancy (see FDA inserts for NS and LR in Appendix 1 and Appendix 2, respectively), the recommended use of crystalloid fluid for resuscitation of pregnant women with septic shock,¹² and the absence of data supporting a

relative difference in efficacy or safety for use of NS versus LR on the developing fetus during any trimester,⁴⁹ there is no specific need to exclude pregnant women from the interventions to be tested in this study beyond the requirements for enrollment under “exception from informed consent”. In addition, since 2012, none of the 1,420 patients treated for sepsis in the CHOP ED has had a positive pregnancy test. Therefore, because waiting for biochemical testing for pregnancy (e.g., urine β -HCG) would either cause most post-pubertal female patients become ineligible for enrollment (due to receipt of >40 mL/kg of fluid) or delay fluid resuscitation (putting potential subjects at risk of harm) *and* given the extremely low risk for diagnosing pregnancy in this patient population *and* given the safe use of both NS and LR in pregnancy, there will not be a requirement to delay study enrollment while awaiting results of a pregnancy test. Any subject enrolled in the study who is subsequently determined to be pregnant as part of routine clinical care, which at CHOP includes testing for pregnancy in all female patients of child-bearing age, will be immediately withdrawn from this study.

- 3) Known prisoner as determined by routine social history disclosed by patient and/or LAR (or other accompanying acquaintance)
- 4) Known allergy to either normal saline or lactated Ringer's as determined by routine allergy history disclosed by patient and/or LAR (or other accompanying acquaintance) or as indicated in the medical record
- 5) Indication of prior declined consent to participate based on presence of a “PRoMPT BOLUS Opt-Out” bracelet with appropriate messaging embossed into the bracelet (see IRB study 17-013950) or the presence of the patient's name on an opt-out list that will be kept up-to-date and checked prior to randomization.

Concurrent participation in another interventional trial will not be considered an exclusion criteria because such co-enrollment is not expected to impact the feasibility aims and outcomes for this study.

Subjects that do not meet all of the enrollment criteria may not be enrolled. Any violations of these criteria must be reported in accordance with IRB Policies and Procedures.

4 STUDY PROCEDURES

4.1 Screening Visit

Patients will be screened at arrival to the ED (i.e., at ED triage) and continuously throughout the ED course for presence of eligibility criteria. Referrals for potential subject enrollment will be made by the ED care team if there is clinician concern for septic shock and need for crystalloid fluid resuscitation assessed by the care team. Although all members of the ED care team may participate in subject referral, a member of the study team will review and concur with the treatment team's eligibility assessment prior to enrollment of the subject. To ensure rapid and appropriate eligibility and enrollment, ED staff (including ED attendings and fellows) will be included as study co-investigators and be trained regarding study enrollment criteria and procedures. Once patients are determined to be eligible, the following study procedures will occur:

- Informed Consent (if time permits) or determination of EFIC
- Randomization

In addition, review of the daily ED triage logs and use of the ED sepsis pathway order set will be performed by study staff to determine potentially eligible patients who were not enrolled. The reason for non-enrollment for all eligible patients will be determined by querying the attending physician of record and/or relevant members of the clinical care team.

4.2 Intervention Phase

The intervention phase will start immediately following the patient's first 20 mL/kg and randomization has been determined, and will end at 11:59 pm on the calendar day following randomization. During this period, the follow study procedures will occur:

- Dispense study fluid
- Monitor study fluid adherence
- If enrollment after EFIC, review inclusion/exclusion criteria
- If enrollment after EFIC, inform subject and LAR of study enrollment (as soon as feasibly possible)
- Medical record review
- Adverse event reporting

4.3 Follow-up Phase

The follow-up phase will start after 11:59 pm on the calendar day following randomization and will end at hospital discharge or 90 days following randomization, whichever comes first. During this period, the following study procedures will occur:

- Open-label fluid treatment
- If enrollment after EFIC and not accomplished during intervention phase, inform subject and LAR of study enrollment (as soon as possible)
- Medical record review
- Adverse event reporting
- Outcome assessment

4.4 Concomitant Medication

All prior and concomitant use of antibiotics, acyclovir, corticosteroids, bicarbonate, parenteral calcium, blood products, crystalloid and colloid fluids (including hypertonic saline), mannitol, intravenous immunoglobulin, diuretics, non-steroidal anti-inflammatory medications (NSAIDS), unfractionated or low-molecular weight heparin, vasoactive infusions (i.e., dopamine, dobutamine, epinephrine, norepinephrine, phenylephrine, milrinone, vasopressin) within one day prior to the screening visit and through the end of the study will be recorded. The dates of administration, dosage, and reason for use will be included.

4.5 Rescue Medication Administration

Open-label use of hypertonic saline, mannitol, unfractionated or low-molecular weight heparin, systemic or local tissue plasminogen activator (tPA), or other “blood thinner”, parenteral calcium, and parenteral bicarbonate will be recorded, including dates of administration, dosage, and reason for use.

4.6 Subject Completion/Withdrawal

Subjects may withdraw from the study at any time without prejudice to their care, including following notification of study enrollment under EFIC. Subjects may also be discontinued from the study at the discretion of the Investigator (at any point) for lack of adherence to study treatment or at the discretion of the attending physician of record (during the intervention phase only) if his/her clinical judgment deems it no longer safe to continue to administer either NS or LR. The Investigator may also withdraw subjects to protect the subject for reasons of safety or for administrative reasons. It will be documented whether or not each subject completes the clinical study. If the Investigator becomes aware of any serious, related adverse events after the subject completes or withdraws from the study, they will be recorded in the source documents and on the CRF.

4.6.1 Early Termination Point

Subjects who withdraw from the study will have all procedures enumerated for the follow-up phase in Section 4.3 performed at the early termination point (rather than at hospital discharge or study day 90).

In addition, subjects randomized to LR in this unblinded study for whom routine, clinician-directed physical and/or laboratory assessment reveals the following criteria within the up-

to-48 hour time window of the intervention phase will not be required to receive additional study fluid as part of this protocol and will be transitioned to an appropriate fluid as determined by the discretion of the treating clinical team. Recognizing that hepatic and renal injury are a) common in septic shock, b) often improved by fluid resuscitation, and c) vary along a spectrum of mild dysfunction (common) to severe failure (uncommon), stopping criteria are defined when either an immediate unsafe condition is noted or when persistent or worsening organ injury indicates that continued LR administration may be cumulatively unsafe (e.g., potassium administration despite worsening oliguria or lactate administration despite worsening hepatic function).

- Hyperkalemia defined as blood potassium >6 mEq/L confirmed on immediate repeat testing
- Hypercalcemia defined as blood total calcium >12 mg/dL or ionized calcium >0.35 mmol/L confirmed on immediate repeat testing
- Severe hepatic impairment defined as rise in blood ALT to $>10,000$ U/L or total bilirubin >12.0 mg/dL
- Severe renal impairment defined as initiation of renal replacement therapy (continuous or intermittent hemodialysis or peritoneal dialysis) or urine output <0.5 ml/kg/hr for 16 hours

NOTE: Hepatic impairment was defined as a fulminant rise in ALT or total bilirubin because other markers of liver function are not commonly recommended for use in pediatric septic shock. For example, an acute elevation in INR is more commonly indicative of hematologic dysfunction than hepatic impairment in pediatric septic shock.⁵⁰

NOTE: Urine output <0.5 ml/kg/hr for 16 hours indicates renal injury (“I”) in the pRIFLE scoring system and stage II kidney injury in the KDIGO scoring system.⁵¹ Creatinine and creatinine clearance will not be used as stopping criteria in the absence of oliguria or initiation of renal replacement therapy because intermittent lab testing may limit the utility of these measurements compared to continuous urine output monitoring and blood creatinine is a poor proxy for a patient’s handling of potassium in that most acute kidney injury in sepsis is caused by acute tubular necrosis, which promotes electrolyte wasting despite a rise in blood creatinine. As an example, in a prior randomized trial of NS versus LR following kidney transplant (as a model of severe acute kidney injury), 19% of patients in the NS developed hyperkalemia >6 mEq/L compared to 0% in the LR group.⁵² Consequently, urine output is the most useful clinical indicator of potential electrolyte retention.

The laboratory values noted above, including potassium, total calcium, ionized calcium, ALT, and bilirubin, will be ordered as determined to be clinically indicated by the treating clinical team rather than prescribed by this study protocol. Because patients with septic shock have wide variability in illness severity and clinical course, including large differences in the amount and timing of fluid administration, pre-specifying which laboratory values to obtain and when to obtain them could result in additional unnecessary phlebotomy and/or access of indwelling lines both of which would impose additional harm (e.g., pain) and risk (e.g., central-line associated bloodstream infection risk increases with additional line accesses) that may not have been experienced outside of the study. Therefore, rather than pre-specifying in the study protocol the laboratory values to obtain

and the time points or timeframe at which to obtain them, the study protocol will utilize the institution's existing laboratory recommendations within the clinical sepsis pathway, which includes potassium and total calcium at least every 12 hours, ionized calcium every 2 hours (as part of blood gas analysis), and ALT and bilirubin every 24 hours for patients with active septic shock admitted to the pediatric intensive care unit (with more frequent laboratory assessments in the subset of patients with more severe illness undergoing ongoing fluid [and other] resuscitation). At CHOP, there are no hospital guidelines for ongoing management of patients treated for septic shock in the ED who are subsequently admitted to the floor following resolution of shock. It is anticipated that ongoing fluid resuscitation outside of the ED setting will be almost exclusively limited to patients who require admission to the PICU, such that the existing clinical sepsis pathway will prompt clinicians to ascertain laboratory values appropriately in those patients at risk for fluid-related abnormalities for whom study fluids will no longer be recommended. The timeframes included within the clinical sepsis pathway provide adequate windows to re-assess safety of ongoing study fluid administration because these potential adverse laboratory effects are related to cumulative fluid administration rather than any one particular fluid bolus.

For subjects randomized to either NS or LR in whom routine, clinician-directed physical and/or laboratory assessment reveals clinical concern for hypersensitivity to the study fluid to which they were randomized, will not be required to receive additional study fluid as part of this protocol within the up-to-48 hour time window of the intervention phase.

Any subjects who meet the above “stopping criteria” will remain in the study for data collection and outcome assessment. Clinician-prescribed fluid administered within the intervention phase will continue to be recorded, including any potential continued use of LR and/or alternative fluid.

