3.1.3 Follow-up Phase

After 11:59 pm on the calendar day following randomization, no further study fluid will be administered solely for research purposes and all care, including any subsequent crystalloid

fluid administration, will be at the discretion of the clinical team. The follow-up phase will continue for the duration of the hospitalization or up through 90 days following study enrollment, whichever comes first. Final determination of subject study completion versus withdrawal, as well as assessment of vital status and clinical outcomes will occur at hospital discharge or 90 days following study enrollment, whichever comes first.

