5 STUDY EVALUATIONS AND MEASUREMENTS

5.1 Screening and Monitoring Evaluations and Measurements

5.1.1 Medical Record Review

The following variables will be abstracted from the medical chart (paper or electronic).

- Name
- Medical record number
- CSN number
- Date/time ED arrival and triage
- Date/time of transfer/discharge from the ED
- Date/time of hospital admission
- Date/time of PICU admission
- Date of birth
- Race
- Ethnicity
- Comorbid medical/surgical conditions
- Pre-hospital medications
- Date, time, and volume of all study fluid administration
- Date, time, and volume of all non-study parenteral fluid administration, including all crystalloids, colloids, blood products, medications, continuous infusions, and flushes
- Total daily recorded volume administered (all “in’s”) and excreted/removed (all “out’s”)
- Date/time of medications/pharmaceuticals administrated during ED and hospitalization
- Laboratory tests (including date/time and results)
- Microbiology tests
- Radiological tests

- Date/time of PICU transfer/discharge
- Date/time of hospital discharge
- Vital status at hospital discharge, study withdrawal, or 90 days following randomization, whichever comes first

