5.3 Efficacy Evaluation

This pilot study will not be powered to determine efficacy. However, the following efficacy outcomes planned for use in a subsequent large pragmatic trial will be measured:

- All-cause hospital mortality (censored at 90 days following randomization), measured as vital status at hospital discharge
- Hospital-free days, measured as the number of calendar days alive and out of the hospital between randomization (day 0) and day 27. Patients who die prior to hospital discharge will be recorded as “zero” hospital-free days. Because follow-up will not proceed after hospital discharge, patients who may have died after hospital discharge but before day 27 will be recorded as having as many hospital-free days up to day 27 as if they had survived to day 27.
- New inpatient dialysis, measured as treatment (or intention to treat if subject does not tolerate treatment) with any renal replacement therapy (including slow continuous ultrafiltration, continuous or intermittent hemodialysis, hemofiltration, or hemodiafiltration, or peritoneal dialysis) that was not a continuation of pre-hospital chronic therapy.
- Hospital length of stay, measured as the number of calendar days between ED arrival and ED or hospital discharge (whichever occurs later).

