6.3.3 Efficacy Analysis

Efficacy endpoints will be tracked between groups as part of this pilot study, but no formal statistical comparisons will be undertaken due to insufficient statistical power. As part of our secondary feasibility analysis, however, we will determine the proportion of patients with complete data available for each efficacy endpoint listed in Section 5.3 to ensure that it is indeed feasible to capture the efficacy outcome measures planned for a subsequent large multicenter trial.

For subjects who may withdraw prior to death and prior to hospital discharge and for whom permission is not granted for continued follow-up of associated clinical efficacy outcomes, the National Death Index will be queried for survival status. According to FDA regulations, when a subject withdraws from a study, the data collected on the subject to the point of withdrawal remains part of the study database and may not be removed. If a subject withdraws from the interventional portion of a study and does not consent to continued follow-up of associated clinical outcome information, the investigator must not access for purposes related to the study the subject's medical record or other confidential records requiring the subject's consent. However, an investigator may review study data related to the subject collected prior to the subject's withdrawal from the study, and may consult public records, such as those establishing survival status

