In addition, the LAR for each subject enrolled via EFIC will be approached as soon as feasibly possible to inform of subject study enrollment and provided the opportunity to continue or withdraw from further study participation. To facilitate this discussion, we will provide the LAR with a “Post-Enrollment Opt-Out Information Sheet” which will summarize the details of the study, including that the subject was enrolled and treated without their consent (as there was no time to obtain it), that the IRB has approved an exception from informed consent for the study, and what the procedures for continued participation will be required (i.e., possibly additional study fluid and medical record review). In addition, the “Post-Enrollment Opt-Out Information Sheet” will disclose that continued participation is voluntary, not necessary to continue to receive care at CHOP, and that subjects can withdraw without penalty or loss of benefits to which the subject is

otherwise entitled. The LAR will also be provided with the prospective Informed Consent Form as a means of providing complete information about what this study involves, though the LAR will not be asked to sign the Informed Consent document. In order to document this encounter, we will ask the LAR to either sign the Post-Enrollment Opt-Out Information Sheet if physically present or have a study team member sign the form if the discussion occurs over the phone. We acknowledge that the LAR's signature will neither constitute nor substitute for informed consent, as these patients would have been enrolled under EFIC. However, because of concerns raised by potential PECARN sites for a possible future multicenter trial and our own ethical interests, we feel it is important to document that the study indeed discussed the details of the study with the subject/LAR and provided an opportunity to opt-out/withdraw by asking the LAR to sign that this discussion took place. Whether the subject/LAR chooses to continue in the study post-enrollment or not, we will document their decision on the "Post-Enrollment Opt-Out Information Sheet" to acknowledge this discussion.

For subjects enrolled via EFIC, if the subject's LAR or family member could not be informed of the subject's participation prior to the subject's death, they will be informed after the subject's death.

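### Sections 4.6.1 and 5.1.1 close outcome assessment at withdrawal for every withdrawing subject, while 6.3.3 implies that follow-up continues unless it is refused

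*Combined protocol and SAP*

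**What the plan says.** Two sets of passages in the combined protocol and SAP govern what happens to outcomes after withdrawal.

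**Assessment at the withdrawal date.** Section 4.6.1: "Subjects who withdraw from the study will have all procedures enumerated for the follow-up phase in Section 4.3 performed at the early termination point". It adds in brackets that this is "rather than at hospital discharge or study day 90". The Section 4.3 procedures include medical record review, adverse event reporting and outcome assessment. The abstraction list in Section 5.1.1 agrees: "Vital status at hospital discharge, study withdrawal, or 90 days following randomization, whichever comes first".

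**Assessment at discharge or day 90.** Section 3.1.3 says that "assessment of vital status and clinical outcomes will occur at hospital discharge or 90 days following study enrollment", whichever is earlier, and does not name withdrawal as a time point. Section 5.3 defines mortality as "All-cause hospital mortality (censored at 90 days following randomization), measured as vital status at hospital discharge", counts hospital-free days to day 27, and defines new inpatient dialysis and length of stay over the hospital stay. Section 6.3.3 then gives a special rule for a subset: "For subjects who may withdraw prior to death and prior to hospital discharge and for whom permission is not granted for continued follow-up". For that subset, survival is sought from the National Death Index and study use of the medical record is barred.

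Section 4.6 lets the Investigator remove a subject for non-adherence, safety or administrative reasons, without any refusal by the family. Section 9.6.3 describes the post-enrollment discussion, in which the representative is "provided the opportunity to continue or withdraw from further study participation".

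**The concern.** Section 6.3.3 needs a special rule only if the remaining withdrawn subjects are still followed. Section 4.6.1 leaves nobody in that remaining group, because it makes the final assessment at withdrawal for all. Study staff cannot apply both rules to a withdrawn child whose chart may still be read.

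At stake are outcomes that are available but would not be collected. Study fluid ends within 48 hours of randomization, whereas the Section 5.3 outcomes run to discharge, day 27 or day 90. A subject withdrawn early and assessed only then has most of the outcome window unobserved.

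This matters to the pilot because Section 6.3.3 will report the proportion of patients with complete data for each efficacy endpoint, to show that those endpoints can be captured in the larger trial. The conflict leaves unclear what will be collected for withdrawn subjects, and so what that proportion will mean.

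**Working it through.** The plan states no figure on this point, so the check sets the passages side by side by type of subject and then sizes the affected group.

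**Who is affected**

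| Subject | 4.6.1 and 5.1.1 | 6.3.3, with 3.1.3 and 5.3 | Conflict? |
|---|---|---|---|
| Meets the LR or hypersensitivity stopping criteria | Kept in the study for outcomes (end of 4.6.1) | Followed to discharge or day 90 | No |
| Withdraws and refuses continued follow-up | Assessed at withdrawal | No record access; National Death Index for survival | No material conflict; the record limit is set by 6.3.3 itself |
| Withdraws and allows follow-up | Assessed at withdrawal | Followed to discharge or day 90 (implied) | Yes |
| Removed by the Investigator under 4.6, no refusal | Assessed at withdrawal | Followed to discharge or day 90 (implied) | Yes |

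**What is truncated in the last two rows**

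- Vital status: dated at withdrawal, not at discharge as 5.3 requires.
- Hospital-free days: 5.3 has rules for death in hospital and for death after discharge, but none for a subject withdrawn while still an inpatient.
- New dialysis: any start after withdrawal is not seen.
- Length of stay: has no end date.

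**Scale: number of withdrawals**

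Inputs: 70 randomized (3.3.2); a criterion of at most 10% (6.3.2). By 5.2.3 and 6.3.2 the numerator of that criterion counts EFIC-eligible patients not enrolled as well as withdrawals, and the denominator is all EFIC-eligible patients, E. If all 70 enter under EFIC (assumption), withdrawals w satisfy

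(E − 70) + w ≤ 0.10 × E, so w ≤ 70 − 0.90 × E.

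- E = 70 (nobody missed): w ≤ 70 − 63 = 7.
- E = 75 (five missed): w ≤ 70 − 67.5 = 2.5, so at most 2.

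Seven of 70 is therefore the most that is compatible with meeting the criterion, not an expected number. It includes refusers, so the group in conflict is smaller still.

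**Scale: deaths**

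Input: 2–6% mortality (1.1), with withdrawn children assumed to have average risk.

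- All 70: 70 × 0.02 = 1.4 to 70 × 0.06 = 4.2 deaths.
- Seven withdrawn: 7 × 0.02 = 0.14 to 7 × 0.06 = 0.42 deaths.
- Chance of at least one among 7: 1 − 0.98^7 = 13% to 1 − 0.94^7 = 35%.

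**The case against.** The best defence is that 6.3.3 already protects the outcome that matters most. Where permission is not granted, the National Death Index supplies survival, and record access is limited on regulatory grounds that no rewording can lift. Subjects who meet stopping criteria stay under observation. Efficacy endpoints receive no formal comparison, and the primary endpoint concerns fluid given during the intervention phase. All of this stands, and it narrows the point to withdrawn subjects who have not refused.

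A reader might infer several stronger things that the documents do not support:

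- **Withdrawn children are generally recorded as alive.** Refusers have the Index query. For the others, a premature vital status arises only if 4.6.1 and 5.1.1 are followed in preference to 6.3.3.
- **Permission for follow-up is never sought.** Section 9.6.3 describes a choice to continue or withdraw and shows no separate question, but the opt-out sheet is not in the documents. The most that can be said is that the route to the permission in 6.3.3 is not shown, nor how silence is treated.
- **Completeness will be overstated.** No passage says that a value taken at withdrawal counts as complete, and read strictly the 5.3 definitions would exclude it. The rule is unstated, which is reason enough to state it.
- **The mortality stop rule is compromised.** Section 6.5 requires an imbalance of about six deaths, while 1.4–4.2 are expected in total, and deaths are to be monitored continuously. A shift of under half an expected death does not change that materially.

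What remains is that nothing except 4.6.1 and 5.1.1 stands in the way of chart follow-up for subjects the Investigator removes, and those two sections do so without exception.

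**Conclusion.** The point holds in a limited form. Sections 4.6.1 and 5.1.1 conflict with 6.3.3, 3.1.3 and 5.3 for withdrawn or discontinued subjects who have not refused follow-up. Followed as written, 4.6.1 cuts short four outcomes that the chart could supply and leaves the meaning of the completeness analysis open for these subjects.

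The size is modest: no more than 7 of 70 subjects if the 10% criterion is met, with 0.14–0.42 expected deaths among them. This assumes that all 70 enter under EFIC, that no eligible patient is missed, that nobody who withdraws refuses follow-up, and that withdrawn children have average risk. The first three make 7 an upper bound. The last is untested, since removal for safety or non-adherence may not be unrelated to outcome. It would be tempting to say that one missed death would be a large share of all deaths. That is conditional on a death being missed, and the chance of even one death among 7 withdrawals is 13–35%.

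Refusers and subjects who meet the stopping criteria are outside the point, and the primary-endpoint definition and the Section 6.5 rule are not materially affected. It is still worth correcting, because outcome capture is one of the things this pilot sets out to test.

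**What to change.** - **4.6.1 and 5.1.1:** limit the early-termination assessment to subjects for whom continued chart review is refused. State that all other withdrawn or discontinued subjects are assessed at hospital discharge or day 90, as in 3.1.3.
- **6.3.3:** count an endpoint as complete only if it is observed to its Section 5.3 time point. State how National Death Index results enter a mortality endpoint defined at hospital discharge, since the Index gives survival status only.
- **9.6.3:** have the post-enrollment discussion record separately whether study fluid may continue and whether chart review may continue, if the sheet does not already do so.

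The cost is protocol wording and possibly IRB review of one form. No visits or tests are added, because the data come from the chart.
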